3.2 Study Outcome Measures

3.2.1 Behavioral Measures

1. PRIMARY OUTCOME: The Hospital Anxiety and Depression Scale (HADS) will be used to measure emotional distress/well-being. The score for each of the two components will be summed to yield a composite score. The severity of emotional distress will be defined as normal range (0-7), mild (8-10), moderate (11-14) or severe (15-20).²⁵ Pre minus post intervention score will be assessed.
2. EXPLORATORY OUTCOME: The Mental Health Continuum Short Form (MHC-SF), which measures psychological and social well-being, will be used to assess improvements in two forms of human flourishing or happiness, hedonic (self-gratification) and Eudaimonic (having a noble purpose) well-being.²⁷
3. EXPLORATORY OUTCOME: PROMIS-SF measures will be collected to assess ancillary symptoms in the domains of: fatigue, sleep disturbance, sleep related impairment, and pain interference.
4. EXPLORATORY OUTCOME: The PCL-M is a frequently used instrument to screen for PTSD in the military population, correlates well with a clinical interview and has been shown to be responsive to symptom change.²⁴

3.2.2 Biological Measures

The primary biological outcome will be telomerase activity determine using the telomere repeat amplification protocol (TRAP), performed as previously described with minor modification.^{28,29} Isolated PBMC are suspended in Chaps lysis buffer and telomerase extract obtained. Extracts are incubated to build telomere repeats, resulting in the product generated due to telomerase activity. To visualize, the PCR reaction included a labeled primer to amplify signal. The PCR product is then run in an acrylamide gel and detected by fluorescent imaging. Calculation of telomerase product generated (TPG) per 10,000 PBMC is performed using ImageQuant software, which takes the fluorescence intensity within a specified parameter and yields a numerical value representing TPG per 10,000 cells. Telomere length will be determined using real time quantitative polymerase chain reaction (qPCR) methodology as described previously with minor modifications.^{30,31} Peripheral blood mononuclear cells (PBMC) are isolated and genomic DNA extracted. Using the standard curve method, cycle threshold (CT) values are plotted on a standard curve of human genomic DNA to estimate an ng/microliter concentration value. Telomere length values are expressed as the ratio of the estimated concentration generated by PCR of the telomere gene (T) divided by the hemoglobin single (S) copy gene = (T/S).

4 STUDY DESIGN

4.1 Basic Design Characteristics

This is a pilot, randomized, double-blinded, sham controlled study on the effect of transcutaneous electrical nerve stimulation on emotional and cellular wellbeing. This is a single center study and all visits will occur at OCNS.

Subjects will be asked to use the CES device daily for 8 weeks. They will be provided with a tracking diary to record the start and stop time of usage daily. Device must be used at approximately the same time of day. Failure to comply is a violation of study protocol and will result in subject withdrawal (see 5.6.1).

4.2 Study Population

Approximately 55 male subjects will be screened in an effort to obtain 22 subjects in each treatment group after randomization. Due to the difficulty with recruitment of eligible Veterans in this feasibility pilot, the study period was extended and non-Veterans meeting the other inclusion criteria were recruited. The study enrollment was limited to 24 completed subjects based on insufficient resources to complete the study beyond the extended recruitment period.

4.3 Study Timeframe

The study timeframe consists of a screening period of 1-2 weeks (commencing between Week -2 to Week -1 and ending on Week 1; see 7.1 and 7.2) followed by an 8-week treatment period (Week 1-Week 8). A flowchart showing the study schedule is provided in **Error! Reference source not found..**

[figure not shown]
The expected duration of subject participation is about 8-10 weeks..

4.4 Randomization and Blinding

This is a randomized, double-blinded, sham controlled study. The active and sham devices are identical in appearance and will only differ by the labeling of a unique serial number. In the sham devices, the electrodes attached to the device will be inactive. The subjects will be instructed that the device is set to a low level so that the current is not detectable but still effective. The current will not be detectable in both active and sham devices in order for adequate blinding to occur.

To ensure that the allocation of subjects to treatment is properly concealed, the PI and research personnel will not know which devices are active or sham. The sponsor will provide the code to determine which devices are active and which are sham. Code will be in a sealed envelope that will not be opened until the end of data collection.

Schematic of Study Design

5 STUDY ENROLLMENT AND WITHDRAWAL

55 Veterans with symptoms of mild to moderate anxiety and depression, in the absence of a psychotic disorder, will be recruited in order to complete 22 subjects per treatment group based on an estimated 25% rate of subject attrition.

5.1 Subject Inclusion Criteria

In order to be eligible to participate in this study, an individual must meet all of the following criteria:

1. Male, Veteran or non-Veteran
2. Within the age range of 18-40 years old
3. On a stable regimen for anxiety, depression, psychiatric or mental health treatment (pharmacological or non-pharmacological) for the past 3 months
4. No active suicidal ideation or psychosis (including schizophrenia and bipolar disorder)
5. No uncontrolled or progressive severe medical illness (e.g., cancer, uncontrolled diabetes mellitus, active cardiac disease)
6. No use of a pacemaker or any other implanted electrical device
7. No alcohol consumption greater than 2 units daily
8. No daily use of illicit drugs or marijuana
9. Ability to independently complete the in-person study questionnaires and sign ICF without assistance
10. Willing to comply with all study procedures and be available for the duration of the study
11. No participation in another clinical trial study

5.2 Subject Exclusion Criteria

An individual who meets any of the following criteria will be excluded from participation in this study:

1. Not male
2. Younger than 18 years old or older than 40 years old
3. Not on a stable regimen for anxiety, depression, psychiatric or mental health treatment (pharmacological or non-pharmacological) for the past 3 months

-
4. Active suicidal ideation or psychosis (including schizophrenia and bipolar disorder)
 5. History of inpatient treatment or suicidal ideation within the last year
 6. Use of a pacemaker or any other implanted electrical device
 7. Current alcohol and/or substance abuse of illicit drugs or marijuana
 8. Unable to independently complete the in-person study questionnaires and sign ICF due to impaired cognitive function
 9. Unwilling to comply with all study procedures
 10. Unavailable for the duration of the study
 11. Current participation in another clinical trial study
 12. Any other condition that the investigator believes would jeopardize the safety or rights of the subject or would render the subject unable to comply with the study protocol or make use of acquired data non-analyzable

5.3 Strategies for Recruitment and Retention

Study participants will be recruited with flyers on UCLA and VA campuses, Internet web advertisements posted on non-interactive Facebook pages and Craigs List, and through direct contact from GLA VA physicians. Most subjects are expected to be recruited from the VA Physical Medicine and Rehabilitation clinic and from other primary providers in ancillary clinics at the VA. Physicians in these clinics are aware of this research study and will give information about who to contact if a Veteran is interested. Physicians will refer the potential study participants to the study team.

Subjects will be compensated for study participation as follows:

\$50.00 for completing screening visit 1, \$50.00 for completing the mid-study visit 2 and questionnaire completion, and \$100.00 for the final visit and completing the final set of questionnaires.

Only subjects who complete a minimum of 5 of 7 days per week compliance will be eligible to complete the final visit and thus be eligible for that payment. Subjects enrolled in study will be contacted weekly to assure subject compliance.

Parking will be provided at all visits.

The stipend payment subjects will receive will be up to \$200.00. If the subject withdraws from the study before finishing, that person will be paid for the study visits completed according to the schedule above.

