2.3.1 Potential Risks

The most common side effects of the device are dizziness, headache, and local skin irritation. Dizziness and headache most commonly occur at higher current levels but will be minimized by having the first electrical stimulation session performed at the research center to make sure the study protocol is tolerated. Subjects who cannot tolerate the study protocol will be dropped from the study. Phlebotomy has a low risk of bruising, swelling or pain at the site, and a very low risk of infection.

The collection of data contains the inherent risk of loss of privacy. This risk will be minimized by adequate training of all study staff according to institutional guidelines, use of unique subject identifiers, and by keeping data in password protected computer databases and/or locked cabinets. An informed consent document was approved by the local Institutional Review Boards at UCLA and a recruitment waiver was obtained from the IRB at the Greater Los Angeles VA. All subjects will read and document understanding of the consent form prior to enrolling in the study.

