5.6 Subject Withdrawal

Study participation is voluntary and subjects have the right to withdraw from the study at any time. The investigator may terminate a subject's participation if necessary.

5.6.1 *Reasons for Withdrawal*

Subjects are free to withdraw from participation in the study at any time upon request.

An investigator may terminate a study subject's participation in the study if:

- Any clinical AE or SAE, laboratory abnormality, or other medical condition or situation occurs such that continued participation in the study would not be in the best interest of the subject.
- The subject meets an exclusion criterion (either newly developed or not previously recognized) that precludes further study participation.
- Non-compliance with study protocol

5.6.2 *Handling of Subject Withdrawals or Subject Discontinuation of Study Intervention*

An adverse events report will be collected from subjects who choose to withdraw from the study. Subjects will be required to return study device to research personnel.

In the event of an (S)AE, every effort will be made to obtain follow-up data on any subject who discontinued device treatment due to an (S)AE. To the extent possible, any withdrawn subject will be followed until the (S)AE has resolved.

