7.3 Intermediate Study Visit (Visit 2)

This visit will occur at the Oppenheimer Family Center for Neurobiology of Stress. This visit will take approximately 1 hour and will occur Week 4 ± 1 week. Subjects must complete this set of study questionnaires:

- Hospital Anxiety and Depression Scale (HADS)
- Positive and Negative Affect Schedule Short Form (PANAS-SF)
- Perceived Stress Scale (PSS)
- Columbia-Suicide Severity Rating Scale (C-SSRS) Self Report Screener - Since Last Contact
- Patient Reported Outcomes Measurement Information System (PROMIS-29)

Subjects will have vital signs and weight measured by a nurse. Adverse events and concomitant medication report will be collected as well. The study coordinator will collect the tracking diary for weeks 1-4 and provide another tracking diary to complete for weeks 5-8.

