7.4 Final Study Visit (Visit 3)

This visit will occur at the Oppenheimer Family Center for Neurobiology of Stress. This visit will take approximately 2 hours and will occur after 8 weeks of

treatment, Week 8 + 1 week. Subjects will be asked to bring the CES device to return. The study coordinator will collect the tracking diary for weeks 5-8. The subjects must complete the final set of questionnaires:

- Mini International Neuropsychiatric Interview (MINI)
- Hospital Anxiety and Depression Scale (HADS)
- Mental Health Continuum Short Form (MHC-SF)
- Patient Reported Outcomes Measurement Information System (PROMIS-29)
- Positive and Negative Affect Schedule Short Form (PANAS-SF)
- Connor-Davidson Resilience Scale (CD-RISC)
- Perceived Stress Scale (PSS)
- Patient Health Questionnaire (PHQ)
- Columbia-Suicide Severity Rating Scale (C-SSRS) Self Report Screener - Since Last Contact
- Impression of Global Improvement Scale

The subjects will have vital signs and weight measured and have the final blood draw performed by a nurse. Adverse events and concomitant medication report will be collected as well.

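### The compliance rule in Section 5.3 closes the only visit that measures week-8 HADS, so the planned intention-to-treat analysis lacks primary-outcome data that could have been collected

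*Combined protocol and SAP*

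**What the plan says.** - **Condition on the final visit (5.3).** "Only subjects who complete a minimum of 5 of 7 days per week compliance will be eligible to complete the final visit". The sentence then makes the final payment a consequence of that eligibility, so the condition falls on the visit itself and not only on the money.
- **Where HADS is measured.** HADS is listed at baseline (7.2), at week 4 (7.3: "Subjects must complete this set of study questionnaires") and at week 8 (7.4: "The subjects must complete the final set of questionnaires"). The primary outcome in 3.2.1 is the pre-minus-post change in the combined score, so it needs Visit 3.
- **Non-compliance.** Section 4.1: "Failure to comply is a violation of study protocol and will result in subject withdrawal". Section 5.6.1, to which 4.1 refers, lists non-compliance under the words "An investigator may terminate a study" subject's participation, which is discretionary.
- **After withdrawal (5.6.2).** "An adverse events report will be collected from subjects who choose to withdraw from the study", and the device is returned. The only wider provision is that "every effort will be made to obtain follow-up data on any subject who discontinued device treatment due to an (S)AE"; it is limited to adverse-event discontinuations and does not name HADS.
- **Other removals.** Section 2.3.1: "Subjects who cannot tolerate the study protocol will be dropped from the study". Sections 5.4 and 6.4 add removals for increased suicidal thoughts and for opiate use.
- **Analysis.** Section 10.2 plans intention-to-treat and completer analyses of the behavioural measures without saying which is primary. Section 10.2.1 specifies a contrast in a mixed model. No missing-data assumption or sensitivity analysis is stated.

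**The concern.** Device use is observed after randomisation and may be related both to how a participant is doing and to the assigned arm. An intention-to-treat comparison is protected by randomisation only as far as outcomes are known for everyone randomised. Here the plan promises that comparison, yet closes the visit that supplies its endpoint to people chosen by their behaviour on treatment. Some would have been willing to attend, so their missing scores are avoidable.

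What is at stake is the treatment effect on the primary outcome. If non-compliance is related to outcome and occurs at different rates in the two arms, the completer comparison is biased and the mixed model is only partly protected. Section 14 says larger studies are needed, so the rule matters most if it is copied into one.

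**Working it through.** **1. Is there another route to week-8 HADS?** Sections 7.2, 7.3 and 7.4 place HADS at baseline, week 4 and week 8. Section 5.3 closes the week-8 visit to non-compliers, and 5.6.2 supplies no HADS. There is no other route.

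**2. The plan's own figures.** Section 10.1 asks for 22 per group (one-sided alpha .05, d = 0.80, 80% power). A noncentral-t calculation gives 81.7% at 21 per group and 83.3% at 22, so 22 is adequate. Section 5 plans for 25% attrition among 55 recruited: 0.25 × 55 = 13.75, about 14 people. The rule's share of these is not given, so avoidable loss lies between 0 and about 14.

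**3. How strict is the rule?** Assume independent daily use with probability p. Reading (a) requires 5 of 7 days in every one of 8 weeks: P = [P(Bin(7, p) ≥ 5)]^8. Reading (b) requires the same rate on average, 40 of 56 days: P = P(Bin(56, p) ≥ 40).
- p = 0.95: (a) 97%, (b) about 100%
- p = 0.90: (a) 81%, (b) about 100%
- p = 0.85: (a) 54%, (b) 99.7%
- p = 0.80: (a) 28%, (b) 96%

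The wording does not settle which applies, so the rule could remove many participants or almost none.

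**4. Completer bias under no true effect.** Let z be week-8 improvement in SD units, standard normal in both arms. Assume P(lost | z) = 1/(1 + exp(−(a − bz))), with slope b from 0.5 to 2 and a set to give the stated loss. Bias is the mean of z among those retained in the active arm minus the same mean in the sham arm, by Gauss-Hermite quadrature.
- Same loss and same mechanism in both arms: the two means are equal, so bias is 0.
- 12% active, 8% sham: b = 0.5 gives 0.058 − 0.039 = 0.019 SD; b = 2 gives 0.167 − 0.117 = 0.050 SD.
- 30% active, 20% sham (mean 25%, all planned attrition): b = 0.5 gives 0.143 − 0.096 = 0.047 SD; b = 2 gives 0.375 − 0.262 = 0.113 SD.

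If sham loses more, the sign reverses. In simulation (55 randomised as 28/27, an assumption; 6,000 runs per setting), one-sided type I error for completers was 6% to 7% at 12%/8% and 7% to 11% at 30%/20%, against a nominal 5%.

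**5. Mixed model, 30%/20% loss.** With the week-4 score known for everyone (a best case) and a week-4 to week-8 correlation of 0.5 to 0.7:
- Loss depends on the week-8 outcome: bias 0.02 to 0.09 SD, type I error 6% to 9%.
- Loss depends only on the week-4 score: bias 0.000 to 0.003 SD, type I error about 5%.

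**6. The reported result.** Section 13.3 gives falls of 8.8 and 3.64, t = −2.32, p = .013; Section 13.2 gives 13 active and 11 sham completers. The means fit those groups (40/11 = 3.636; 114/13 = 8.77), which suggests completers but does not prove it. With 24 people and three HADS visits, within-subject degrees of freedom are (24 − 2) × (3 − 1) = 44. One-sided p for t = 2.32 at df 44 is .0125, which rounds to .013. A simple t-test at df 22 would give .015, but 10.2.1 specifies a mixed model.

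**The case against.** The strongest reply is that the rule may have cost little. Under the averaging reading, 96% or more would pass at daily use of 0.80 and above, and Section 6.3 supports adherence with daily and then weekly calls. Active and sham devices look identical and the current is meant to be undetectable (4.4, 6.2.1), which makes similar loss in the two arms plausible. Ordinary attrition and the removals in 2.3.1, 5.4 and 6.4 would require a missing-data assumption anyway. The rule acts on device use, not on week-8 HADS. If poor use mainly reflects how the participant was doing at week 4, the planned model copes almost fully. This was also a pilot that its own report calls a feasibility failure.

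All of that stands as a limit on size. It does not remove the structural gap: the endpoint is not sought from people who could give it, and whether loss follows the week-4 score or the later outcome cannot be checked without their week-8 scores.

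Three stronger readings are tempting and are not supported:
- *Data were thrown away, or participants were turned away.* The scores are never collected under the rule. The text reports no refused visit and gives neither the number randomised nor the reasons for loss; a figure is not shown.
- *The bias is large.* Outcome-related loss of 25% confined to the active arm would bias completers by 0.12 to 0.32 SD. Nothing in the documents points to such one-sided loss, and the blinding argues against it.
- *The reported p-value is wrong.* It is consistent with the planned model at df 44.

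**Conclusion.** The point holds as a design weakness worth fixing. Sections 5.3, 5.6.2 and 7.4 together leave week-8 HADS uncollected from randomised participants who could attend, while 10.2 plans an all-randomised analysis. That follows from the text alone.

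The size is unknown. The figures above are illustrations resting on assumed loss rates, an assumed logistic link between loss and outcome, and 55 randomised, although Section 4.2 speaks of about 55 screened. The 30%/20% result is an upper bound for that pattern of imbalance, because it assigns all planned attrition to the rule. For scale, the planned effect is 0.80 SD. A reader might infer that the 8.8 versus 3.64 result is a product of the rule; the documents give no basis for saying so, or for ruling it out.

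**What to change.** **Follow-on protocol**
- In 5.3, remove compliance as a condition of attending Visit 3, and seek week-8 HADS from every randomised participant who has not withdrawn consent.
- Distinguish stopping device use from stopping outcome assessment. Reconcile 4.1 (withdrawal is certain), 5.3 and 5.6.1 (withdrawal is discretionary) on that basis; otherwise opening Visit 3 may recover nobody. State whether outcome assessment continues after the removals in 2.3.1, 5.4 and 6.4. The device-use and safety rules themselves need not change.
- In 10.2, make the all-randomised mixed model (baseline, week 4, week 8) primary and the completer set supportive.

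**Completed trial**
- In 13.3, report the intention-to-treat and completer analyses side by side, labelled, unless the table not shown already does so.

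**Cost.** The completed trial needs a label and an analysis already planned. A follow-on needs wording changes and no new visit type. Each attending non-complier costs up to 100 dollars plus parking and staff time for a two-hour visit; if all of an assumed 25% of 55 attended, payments would be about 14 × 100 = 1,400 dollars. If payment is tied to attendance alone, a financial incentive to adhere is lost, though the calls remain.

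The all-randomised effect may also be smaller, so power need not rise. With all 55 measured, power is 90% if d stays at 0.80, but 71% if a recovered 25% gain nothing (d = 0.75 × 0.80 = 0.60), against 81% with about 41 measured.

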5.4 Reporting Suicidal Ideation

To minimize risk, patients will be selected based on mild to moderate but not severe depression and/or anxiety, and who are on a stable therapeutic regimen (medication, psychotherapy, or stable without treatment) to reduce the risk of harm with a new intervention. Patients will be interviewed for both physical and psychiatric symptoms. Patients with a history of suicide attempt in the past year, who express having an intention of acting on suicidal thoughts as measured by a positive answer to the Columbia-Suicide Severity rating scale questions 4-6, or have other clinical risks on interview deemed by the investigator to be exclusionary will be excluded from the study and referred to a mental health professional, primary care provider, or emergency room after assessment of the patient. If the patient already has a mental health care or primary care provider, the provider will be contacted by the medical staff, with the patient's permission, to update them on the subjects's change in condition. All subjects will be asked at entry to the study to sign a HIPPA release and provide their clinicians contact information, so that this option is available in the event of a clinical emergency. The Veteran's Crisis line number will be provided to all Veteran subjects ([name]). Subjects whose answers to the Columbia screener "since last visit" questionnaire show an increase in suicidal thoughts will be discharged from the study after determination of appropriate follow up as described above. No attempt to control psychiatric medication will be made in this study. Types and doses of medications taken by the subject will be carefully documented and examined in post hoc analyses.

